#### For entire study:

- The **FAS** population consists of the Markedly Improved Patients who were randomised to IKERVIS in Period 2 and received at least one dose of IKERVIS in Period 2 and had at least one post-Month 12 sign or symptom assessment of the study eye during Period 2. This will be the population used for efficacy analyses.
- The **PPS** will be a subset of FAS, restricted to the subjects who fulfill the protocol in the terms of the eligibility, interventions, and outcome assessment. It will be the analysis population for some sensitivity analyses.
- The **Safety population** consists of the Markedly Improved Patients who were randomised to IKERVIS in Period 2 and had at least one post-Month 12 sign or symptom

assessment of the study eye during Period 2. It will be the analysis population for safety analyses to be performed with subjects as treated.

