2. STUDY OBJECTIVES AND ENDPOINTS

2.1. Objectives

The primary objectives of this study are:

- To evaluate the long-term efficacy of a continuous treatment of IKERVIS® (1mg/mL ciclosporin) eye drops in adult dry eye disease (DED) subjects with severe keratitis on corneal sign and DED symptoms, and to estimate the lag time (if any) to improvement in symptoms (if any).
- To assess the ocular surface complications (defined as corneal ulceration, corneal perforation, loss of visual acuity, and ocular infection) over the three-year study period.

The secondary objectives of this study are:

- To evaluate the efficacy parameters (signs and symptoms), the ocular surface complications, and the quality of life over treatment Periods 1 and 2.
- For 12-month markedly improved subjects, to evaluate and compare signs and symptoms evolution in IKERVIS® group versus Vehicle group during the randomised period of the study (Period 2).
- To evaluate the safety and tolerability of IKERVIS® (1mg/mL ciclosporin) eye drops treatment over the three-year study period.

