5. GENERAL CONSIDERATIONS

All measures will be summarized for Overall subjects in Period 1 and by treatment group in Period 2 as well as for the entire study descriptively. Continuous variables will be summarized using descriptive statistics such as number of observations (n), mean, standard deviation, median, minimum, and maximum. Categorical variables will be tabulated using frequency (n) and percent (%).

Unless otherwise specified, the following conventions on decimal places will be followed in reporting numerical results.

Statistic	Reporting Decimal Places
Range (Low Value, High Value)	Recorded decimal places
Mean, Median	Recorded value + 1 decimal places
Confidence interval, standard deviation, standard error	Recorded value + 2 decimal places
P-value	4 Decimal places (ex. 0.0021)

No statistical testing will be conducted for both the efficacy and safety measures for Period 1 in this study.

All data summary/analysis will be performed using SAS Version 9.4 or later. Individual data, including relevant derived variables, will be listed. Additional analyses not specified in this SAP may be conducted if deemed necessary and will be documented in the CSR.

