6. ANALYSIS POPULATION

Analysis populations defined for each analysis period are as follows.

For Period 1:

- The FAS (Full Analysis Set) Period 1 population consists of all enrolled subjects who received at least one dose of the study medication and had at least one post-baseline sign or symptom assessment of the study eye during Period 1. This will be the population used for efficacy analyses of Period 1.
- The **PPS** (**Per-Protocol Set**) **Period 1** will be a subset of FAS, restricted to the subjects who fulfill the protocol in the terms of the eligibility, interventions, and outcome assessment. It will be the analysis population for some sensitivity analyses.
- The **Safety Population Period 1** consists of all subjects enrolled in Period 1 who received at least one dose of the study medication and for whom any follow-up information is available. It will be the analysis population for safety analyses to be performed with subjects as treated.
- The **Sjögren Patients Population** consists of subjects who were known to have diagnostic status of the Sjögren disease based on the medical history obtained at baseline.
- The **Subjects Markedly Improved during Period 1** are defined as FAS subjects who achieve CFS score improvement from baseline of 2 grades or more (unless if the subject had a CFS score of 5 at baseline, the improvement in CFS has to be 3 grades or more) at anytime during Period 1.

For Period 2 and Entire Study:

- The FAS Period 2 (or FAS Entire Study) population consists of all randomized subjects who received at least one dose of the double-masked study medication and had at least one post-Month 12 sign or symptom assessment of the study eye during Period 2. This will be the population used for efficacy analyses.
- The **PPS Period 2 (or PPS Entire Study)** will be a subset of FAS Period 2, restricted to the subjects who fulfill the protocol in the terms of the eligibility, interventions, and outcome assessment. It will be the analysis population for some sensitivity analyses.
- The Safety Population Period 2 (or Safety Population Entire Study) consists of all subjects randomized in Period 2 who received at least one dose of the double-masked study medication and for whom any follow-up information is available in Period 2. It will be the analysis population for safety analyses to be performed with subjects as treated.

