8.1.1. Primary Analysis

For Period 1 analysis, Spearman correlation coefficient and its 95% confidence interval will be calculated for the correlation analysis between change from baseline in CFS score at visit X and SANDE symptoms score at each visit X+i in period 1 using the FAS Period 1 population.

The primary efficacy endpoint analysis result will be presented graphically by plotting Spearman correlation coefficients calculated at each visit. Spearman correlation coefficients will be plotted for the timepoints where more than 2 lagtime correlations are calculated. The plots will have x-axis to show lags, i, and y-axis to show Spearman correlation coefficients as shown in Figure 2, which is for X = Month 3.

Figure 2. A Sample Plot of Correlation between Change from Baseline in CFS Score at Visit X vs. Change from Baseline in SANDE Score at Visit X + i

Spearman Correlation Coefficients Calculated at Month 3

Interpretation of the results from graphical analysis:

- o If any individual graph shows a "bump" or a plateau at any lag > 0 point, as shown in Figure 2, it would be considered as an indication of existence of a lagged symptom response for CFS score at that particular visit X.
- o If there are at least half (50%) of the graphs show lagged symptom responses, we would conclude that dry eye symptoms (measured by SANDE questionnaire) show lagged response improvement in comparison to dry eye sign improvement.

For Period 2 analysis, Spearman correlation coefficient between change from baseline in CFS score at visit X and SANDE symptoms score at each visit X+i, its 95% confidence interval will be calculated by treatment group. The analysis will be based on the FAS Period 2 population.

For long term efficacy, the Entire Study analysis will be performed by repeating the Period 1 analysis for the entire 3 year duration using the FAS Entire Study population.

The analysis details are shown in Table 4 by study period.

Table 4 Analysis of Correlation between Change from Reference Point in CFS Score at Visit X and Change from Reference Point in SANDE Symptom Score at Visit X + i

Study Period / Analysis Population	Reference Point	Visit X	Visit X + i
Period 1 FAS Period 1 subjects	Baseline	Month 3*	Month 3, Month 6, Month 9, Month 12
		Month 6*	Month 6, Month 9, Month 12
		Month 9	Month 9, Month 12
		Month 12	Month 12

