Period 2 FAS Period 2 subjects (by treatment arm)	Month 12	Month 15*	Month 15, Month 18, Month 21, Month 24, Month 27, Month 30, Month 33, Month 36
		Month 18*	Month 18, Month 21, Month 24, Month 27, Month 30, Month 33, Month 36
		Month 21*	Month 21, Month 24, Month 27, Month 30, Month 33, Month 36
		Month 24*	Month 24, Month 27, Month 30, Month 33, Month 36
		Month 27*	Month 27, Month 30, Month 33, Month 36
		Month 30*	Month 30, Month 33, Month 36
		Month 33	Month 33, Month 36
		Month 36	Month 36

Study Period / Analysis Population	Reference Point	Visit X	Visit X + i
Entire Study (Period 1 + Period 2) FAS Entire Study subjects	Baseline	Month 3*	Month 3, Month 6, Month 9, Month 12, Month 15, Month 18, Month 21, Month 24, Month 27, Month 30, Month 33, Month 36
		Month 6*	Month 6, Month 9, Month 12, Month 15, Month 18, Month 21, Month 24, Month 27, Month 30, Month 33, Month 36
		Month 27*	Month 27, Month 30, Month 33, Month 36
		Month 30*	Month 30, Month 33, Month 36
		Month 33	Month 33, Month 36
		Month 36	Month 36

^{*} Spearman correlation coefficients will be plotted

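### The SAP opens the Entire Study analysis set to both arms but states no arm split for the three-year CFS–SANDE correlation that serves the continuous-IKERVIS objective

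*SAP*

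**What the plan says.** The first primary objective, unchanged from protocol to SAP, is "To evaluate the long-term efficacy of a continuous treatment of" IKERVIS (SAP 2.1).

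Protocol 13.2, under the entire-study heading, matches it. Its FAS definition reads: "population consists of the Markedly Improved Patients who were randomised to IKERVIS in Period 2 and received at least one dose of IKERVIS". The per-protocol set (PPS) is a subset of that FAS.

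SAP 6 replaces this with one shared definition: "The FAS Period 2 (or FAS Entire Study) population consists of all randomized subjects" who took masked medication and had a later assessment. The PPS is again a subset. SAP 7.2 confirms that the Entire Study FAS and the Period 2 FAS are the same patients.

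For the primary correlation, SAP 8.1.1 says that "the Entire Study analysis will be performed by repeating the Period 1 analysis for the entire 3 year duration" on the Entire Study FAS. In Table 4 the Period 2 row begins "Period 2 FAS Period 2 subjects (by treatment arm", while the Entire Study row reads "Entire Study (Period 1 + Period 2) FAS Entire Study subjects" with no mention of arm.

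The PPS sensitivity analysis (SAP 8.1.2) and the Entire Study Sjögren analyses (SAP 6 and 8) use sets derived from the same all-randomised definition and state no split either.

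**The concern.** Under the protocol the Entire Study correlation needed no split, because its FAS held only IKERVIS patients. The SAP removed that restriction and put nothing in its place. An analyst who follows 8.1.1 to the letter would report, as the long-term result for continuous IKERVIS, a coefficient from patients of whom a planned 40% spend 24 of the 36 months on vehicle.

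No other row of Table 4 fills the gap. The by-arm Period 2 rows measure change from Month 12, as SAP 4.2.3 also requires, so they do not give three-year change from baseline. The Period 2 sentence in 8.1.1 adds confusion by naming the other reference point: "For Period 2 analysis, Spearman correlation coefficient between change from baseline in CFS score at visit X".

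The lag reading is affected too. SAP 8.1.1 looks for a rise or plateau at any positive lag, with no reference to a confidence interval. In the Month 3 plot, lags 0 to 3 (Months 3 to 12) come from patients all on IKERVIS. Lags 4 to 11 (Months 15 to 36) would come from a 60/40 mix. The treatment composition would change inside the curve being read.

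**Working it through.** **Inputs.** From SAP 3.3: 350 enrolled, 70% = 245 randomised, 147 IKERVIS and 98 vehicle, CFS difference 0.4, SD 1.10, power 80%. The documents give no SANDE standard deviation and no expected correlation, so those are assumed over ranges.

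**The plan's own figure.** With two-sided alpha 0.05 (assumed), z = 0.4 / (1.10 × √(1/147 + 1/98)) − 1.96 = 2.788 − 1.96 = 0.828, which gives power 0.796. The stated 80% reproduces.

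**Vehicle share.** 98/245 = 40%. The set grows from 147 to 245.

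**How many correlations are affected.** Entire Study rows printed in Table 4:

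| CFS visit | Pairs | SANDE after Month 12 |
|---|---|---|
| Month 3 | 12 | 8 |
| Month 6 | 11 | 8 |
| Month 27 | 4 | 4 |
| Month 30 | 3 | 3 |
| Month 33 | 2 | 2 |
| Month 36 | 1 | 1 |
| Total | 33 | 26 |

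Of the 26, 16 have only SANDE after Month 12 and 10 have both measures after it. If all twelve visits from Month 3 to Month 36 are used (an assumption, since the other rows are not printed), there are 12 × 13/2 = 78 pairs. Of these, 4 × 8 = 32 have only SANDE after Month 12 and 8 × 9/2 = 36 have both, 68 in all.

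**Shift if the within-arm correlation ρ is the same in both arms.** For a two-group mixture with standardised mean differences d1 (CFS) and d2 (SANDE), and pq = 0.6 × 0.4 = 0.24:

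pooled r = (ρ + 0.24·d1·d2) / √[(1 + 0.24·d1²)(1 + 0.24·d2²)]

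Take d1 = 0.4/1.10 = 0.364 when CFS is after Month 12, and 0 otherwise. Take d2 from 0 to 0.5 (assumed). Protocol 4.1.1 reports almost no symptom difference in the earlier trials: −13.6 v −14.1 on OSDI, and −12.82 v −11.21 on the discomfort scale.

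| Case | ρ | d1 | d2 | Shift by formula | Simulated Spearman shift |
|---|---|---|---|---|---|
| Both after Month 12 | 0.5 | 0.364 | 0 | −0.008 | −0.004 |
| Both after Month 12 | 0.3 | 0.364 | 0.5 | +0.029 | +0.030 |
| Both after Month 12 | 0 | 0.364 | 0.5 | +0.042 | +0.040 |
| SANDE only after Month 12 | 0.5 | 0 | 0.5 | −0.014 | −0.015 |

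The simulation used 300,000 patients allocated 3:2, CFS on the seven Oxford levels, and assumed baseline grades 3/4/5 of 50/35/15%.

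**Shift if the within-arm correlations differ.** With no mean difference, pooled r is about 0.6·r(IKERVIS) + 0.4·r(vehicle), so it sits 0.4 × (gap) from the IKERVIS value. A gap of 0.1 gives 0.04 and a gap of 0.2 gives 0.08. Simulated Spearman values on the Oxford levels run from −0.034 to −0.072; for example, IKERVIS 0.364 and vehicle 0.183 pool to 0.292. Wider gaps move it further: in a continuous-score simulation with the CFS shift included, 0.288 and 0.001 pool to 0.171.

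**Precision.** The Fisher-z half-width near r = 0 is 1.96/√(n − 3):

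- n = 245: 1.96/√242 = 0.126
- n = 147: 1.96/√144 = 0.163
- n = 98: 1.96/√95 = 0.201

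**The case against.** The strongest reply is SAP 5, which says measures are summarised for all subjects in Period 1 and "by treatment group in Period 2 as well as for the entire study descriptively". That can be read as a by-group rule for the entire study, and the correlation carries no formal hypothesis. SAP 7.7 names IKERVIS/IKERVIS and IKERVIS/Vehicle groups, and SAP 9.2 to 9.4 attach treatment to both Period 2 and the Entire Study. Repeating the Period 1 analysis may mean only its statistic, reference point and plots, because a one-arm period had no split to state. This is why pooling cannot be called certain.

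It does not close the gap. The SAP 5 sentence is ambiguous and general, and 8.1.1 is the specific instruction. Where the SAP wants a split or restriction for the entire study it says so: 9.2 to 9.4 state it, and 9.1 limits the Month 1–36 complication rate to the IKERVIS group. Section 8.1.1 does neither.

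Three further points stand in part:

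- **Small effect.** This is accepted. In the Month 3 plot CFS precedes randomisation, so with equal within-arm correlations the shift is at most about 0.015.
- **Disclosure.** The revision history mentions an updated analysis set, and SAP 10.4 reprints the new FAS and PPS definitions. But the title and lead sentence of 10.4 name only the Safety population, and no reason is given.
- **Unseen text.** The SAS sample code listed for SAP 12 is not visible, and Table 4 as available skips from Month 6 to Month 27. The code might settle the grouping.

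**Conclusion.** The concern holds. The widening of the Entire Study FAS and PPS is certain from the text. The absence of a stated arm split for the Entire Study correlation is also certain. Whether the arms would actually be pooled is unresolved.

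If they are pooled, a planned 40% of the patients behind a primary long-term result are off IKERVIS after Month 12, in 26 of the 33 printed visit pairs. The expected shift is about −0.015 to +0.04 with equal within-arm correlations of 0 to 0.5, and about 0.03 to 0.08 if they differ by 0.1 to 0.2. Both ranges are below the 0.126 half-width at n = 245 and rest on the assumed SANDE difference and correlations. It takes within-arm gaps of roughly 0.3 to move the coefficient by 0.1 or more. The case for correction is the mismatch between population and objective, and the change of treatment mix inside the lag curves, rather than a large numerical bias.

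**What to change.** - Keep the all-randomised set, but state in SAP 8.1.1 and on the Entire Study row of Table 4 that correlations and lag plots are produced by randomised arm. Name IKERVIS/IKERVIS as the result for the continuous-treatment objective. That arm is in substance the protocol's Entire Study FAS.
- Apply the same split to the Entire Study PPS analysis (8.1.2) and the Sjögren analyses (SAP 6 and 8). To agree with SAP 5, state it also for the Entire Study summaries in 8.2.1 and 8.2.2. Protocol 5.3.2.2 already places DEQS in the randomised population, so only the split is at issue there.
- List the FAS and PPS change under its own heading in SAP 10, with the reason.
- Use one reference point for Period 2 in the 8.1.1 sentence and in Table 4.

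The cost is SAP wording and by-arm outputs; no new data are needed. The long-term IKERVIS correlation then rests on a planned 147 patients (half-width about 0.163) instead of 245 (about 0.126), with about 0.201 for the 98 on vehicle. By-arm Sjögren intervals will be wider still, by an amount that cannot be stated because no Sjögren number is planned.

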3. STUDY DESIGN

3.1. General Study Design

This is a phase IIIb, prospective, interventional, multicentre, three-year study to explore the long-term evolution of sign and symptoms, and occurrence of complications in dry eye disease subjects with severe keratitis receiving IKERVIS® (1mg/ml ciclosporin) eye drops. All enrolled subjects will enter a period of 12 months of treatment (Period 1) with open-label IKERVIS® treatment [once daily (QD) into the affected eye(s) at bedtime]. At Month 12 visit, markedly improved subjects will continue the study for an additional 24 months randomized, double-masked treatment period (Period 2) to receive either IKERVIS® QD or vehicle QD (at a ratio of 3:2), Figure 1.

Figure 1. Study Design Diagram

IKERVIS will be used with AT (same AT for all patients) up to 6 times per day

Markedly improved subjects are defined as subjects having a corneal fluorescein staining (CFS) score improvement from baseline of 2 grades or more on the modified Oxford scale [unless if the subject had a CFS score of 5 at baseline, the improvement in CFS has to be 3 grades or more] in the study eye. Subjects who are not markedly improved at Month 12 based on the above definition will be terminated from the study.

This study will be conducted in about 36 sites located in European and non-European countries.

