3.2. Randomization and Masking

Period 1 of the study is open-label, single arm treatment with IKERVIS®. No randomization is needed in Period 1 (from Baseline for the first 12 months of treatment).

At the beginning of Period 2, (ie. the Month 12 visit), subjects who achieve a marked improvement (ie. CFS score improvement from baseline of 2 grades or more [unless if the subject had a CFS

score of 5 at baseline, the improvement in CFS has to be 3 grades or more]) will be randomly assigned (by the IWRS/IVRS) in a 3:2 ratio to receive either IKERVIS® or Vehicle for two years in a double-masked fashion. The randomization will be stratified by region (Europe vs. non-Europe), and the permuted block randomization will be used within each stratum.

The randomization schedule will be generated and implemented using central randomization via Interactive Response Technology (Rave RTSM). Each randomized subject will receive numbered study medication kits as assigned by Rave RTSM.

Treatment assignments during the Double-Masked Treatment Period will be masked to Santen employees (except Drug Supply personnel), study subjects, and Investigators. The investigator should try to avoid breaking the masking codes. However, in case of emergency only, (i.e. serious adverse event [SAE] and only when this information influences the subject's management), the investigator is entitled to unmask the subject by using IWRS, in order to obtain the study medication information (i.e. IKERVIS® or vehicle) to immediately start the appropriate treatment [to be recorded in the source data and eCRF (electronic Case Report Form)]. A record will be made of the date, time and reason for breaking the code. The investigator should inform the Sponsor immediately after unmasking. The details of this unmasking procedure will be described in a separate document. Subjects unmasked for the management of a SAE will be discontinued from the study.

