3.3. Sample Size Determination

The sample size of this study is not planned from a formal sample size calculation since formal statistical hypothesis testing will not be performed for the primary endpoints. In this study, we plan to enroll 350 subjects. Of the 350 subjects, it is estimated that approximately 70% (245 subjects) would become markedly improved in CFS after Month 12 and enter the Period 2 (double-masked randomized period), based on Santen previous IKERVIS studies. With a 3:2 randomization allocation ratio, a sample size of 147 for IKERVIS® and 98 for Vehicle will allow us to detect a difference of 0.4 or more in CFS score with 80% power assuming the standard deviation of the difference is 1.10.

Petroutsos *et al.* (1992) showed that after 6 years of follow-up on DED subjects, a lower-bound of the estimated complication rate was 4% in severe DED subjects. In the current study, 350 subjects treated with IKERVIS® for at least one year would have 95% power to detect at least one ocular complication that occurs at 1% rate with type I error rate of 0.05.

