7.2. Demographics and Other Baseline Characteristics

For Period 1 summary, subject demographics and baseline characteristics will be summarized for the FAS Period 1 population, the Sjögren Patients Population, and the Markedly Improved Subjects in Period 1. The descriptive summary will be repeated for the FAS Period 2 population for each treatment group and overall for Period 2 summary and Sjögren Patients to satisfy FAS Period 2. The Entire Study summary will not be provided because the FAS Entire Study population is same as the FAS Period 2 population.

For subject demographics, the following variables will be summarized:

- Age at enrollment (continuous and categorical: < 65 years or ≥ 65 years)
- Sex (categorical: male or female)
- Ethnicity (categorical: Hispanic/Latino or Not)
- Race (categorical: American Indian or Alaska Native, Asian, Black or African American, Native Hawaiian or Other Pacific Islander, White, or Other)

For baseline characteristics, the following variables will be summarized for study eye (summarize for fellow eye if needed):

- CFS Score on the Modified Oxford Scale (<3 and each category)
- Schirmer test without anaesthesia (<10 mm/5 min or ≥10 mm/5 min)
- Symptom Score (Number of subjects with a score ≥ 2)
- Primary diagnosis (dry eye disease: both eyes or single eye)
- Duration of dry eye disease (years)

- Sjögren Disease status (yes or no) where appropriate
- Alcohol use [yes or no; if yes, ≤ 30 g per day (women) or ≤ 40 g per day (men), > 30 g per day (women) or > 40 g per day (men)]
- Illicit or recreational drug use (yes or no)
- Tobacco use
 - o Yes
 - Ex-smoker (number of packets per year and duration of smoking)
 - Current smoker (number of packets per year and duration of smoking)
 - o No
- Passive tobacco use (yes, no)

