8.3. Subgroup Analyses

For period 1, the clinical subgroup of interest are

- Sjögren patients
- Subjects who experienced marked improvement during Period 1 where marked improvement is defined as CFS score improvement from baseline of 2 grades or more on the modified Oxford scale [unless if the patient had a CFS score of 5 at baseline, the improvement in CFS has to be 3 grades or more] in the analysis eye.

Efficacy analysis of Period 1 will be repeated using this subpopulation.

For Period 2, subgroup analysis by Sjögren patients will be conducted to investigate the treatment effects of the target population across region in Period 2. Other subgroup analyses may be performed as deemed necessary.

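### The Entire Study CFS–SANDE correlations use only patients selected on their own Month 12 CFS change, which lowers the coefficients, most of all at Month 12

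*SAP*

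**What the plan says.** SAP 8.1.1 places three sets of Spearman correlations under the primary analysis: Period 1, Period 2 by arm, and Entire Study. For the last, the "Entire Study analysis will be performed by repeating the Period 1 analysis for the entire 3 year duration using the FAS Entire Study population". Table 4 gives baseline as the reference point and starts the Entire Study rows at X = Month 3, so pairs lying wholly within Months 3 to 12 are computed in this set as well.

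Who is in the set follows from four places:

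- SAP 6: "The FAS Period 2 (or FAS Entire Study) population consists of all randomized subjects who received at least one dose" of masked medication and had a sign or symptom assessment after Month 12. SAP 7.2 confirms that "the FAS Entire Study population is same as the FAS Period 2 population".
- SAP 3.2: randomisation is for "subjects who achieve a marked improvement (ie. CFS score improvement from baseline of 2 grades or more", or 3 grades or more where baseline CFS was 5.
- SAP 3.1: "Subjects who are not markedly improved at Month 12 based on the above definition will be terminated from the study".
- SAP 3.3: "Of the 350 subjects, it is estimated that approximately 70% (245 subjects) would become markedly improved in CFS after Month 12".

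SAP 8.1.1 also sets a reading rule. A bump or plateau at any lag above 0 marks a graph as showing a lagged symptom response, and a lag is concluded when at least half of the graphs do so. The only sensitivity analysis (SAP 8.1.2) uses the PPS, a subset of the same patients. Neither SAP 8.1 nor SAP 10 mentions the selection.

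**The concern.** CFS change from baseline at Month 12 is both the criterion for entering the set and one of the two variables being correlated. Cutting off the poorer part of its range narrows its spread, and a correlation computed on a narrowed range is smaller than in all treated patients. CFS change at other visits is narrowed too, but only as far as it is related to the Month 12 value. The loss is therefore uneven along a lag curve and greatest where the curve meets Month 12.

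Two things are at stake. First, the three-year coefficients can be read as evidence that sign and symptoms are weakly related, which is already the premise in Protocol 4.2, when part of the weakness comes from the randomisation rule. Second, a local low at Month 12 followed by a flat or slightly rising stretch is the kind of shape that the graph rule counts as a lag.

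**Working it through.** **The plan's own figures.** 350 × 0.70 = 245, split 3:2 into 147 and 98. For CFS, SE = 1.10 × √(1/147 + 1/98) = 0.143; 0.4/0.143 = 2.79; power = Φ(2.79 − 1.96) ≈ 0.80, at an assumed two-sided 0.05. The stated 80% reproduces. The documents give no figure for the CFS–SANDE correlation or for the effect of selection.

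**Inputs.** From the documents: the selection rule, 70% retained, SD 1.10, n = 245. Assumed: an unselected same-visit correlation of 0.2–0.5, and several between-visit structures (compound symmetry, AR(1), AR(1) with measurement error, random intercept with AR(1)).

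**Step 1: normal approximation at Month 12.** Keeping the best 70% puts the cut at z = 0.524.

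- λ = φ(0.524)/0.70 = 0.348/0.70 = 0.497.
- Share of variance left: k = 1 − 0.524 × 0.497 − 0.497² = 0.49.
- Correlation after selection: r′ = r√k / √(1 − r² + r²k).

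This takes 0.20 to 0.14, 0.30 to 0.22, 0.40 to 0.29 and 0.50 to 0.38, a loss of about 25–29%.

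**Step 2: graded CFS scale, actual rule.** A simulation on grades 0, 0.5 and 1–5, with 69% retained, narrows the SD of Month 12 CFS change from 1.06 to 0.66, so k = (0.66/1.06)² = 0.39. Spearman falls from 0.27 to 0.17 and from 0.45 to 0.30. The formula with k = 0.39 gives the same two results. Two further no-lag simulations with about 69% selected gave 0.31 to 0.19 and 0.30 to 0.18. The loss here is about 33–40%.

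**Step 3: other visits and curve shape.** Symptoms were tied only to the same-visit CFS, so no lag exists. Example with CFS variance 0.4 stable, 0.4 serial (0.8 per visit) and 0.2 measurement error:

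| | M3 | M6 | M9 | M12 | M15 | M18 |
|---|---|---|---|---|---|---|
| Same visit, all | 0.45 | 0.45 | 0.45 | 0.45 | 0.45 | 0.45 |
| Same visit, selected | 0.40 | 0.40 | 0.38 | 0.30 | 0.38 | 0.40 |
| X = Month 3, all | 0.45 | 0.32 | 0.29 | 0.27 | 0.25 | 0.24 |
| X = Month 3, selected | 0.40 | 0.26 | 0.22 | 0.15 | 0.17 | 0.16 |

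Across all structures, visits other than Month 12 lose about 4–28%, most next to Month 12. With measurement error or a random intercept, the curves from X = Months 3, 6 and 9 dip at Month 12 and recover slightly at Month 15. Under pure AR(1) there is no recovery, only a steeper fall to Month 12 and then a flatter tail (selected set, X = Month 3, r = 0.3: 0.22, 0.18, 0.15, 0.11, 0.10, 0.09). Over all runs the rise is 0.00–0.06. The standard error of a coefficient at n = 245 is about 1/√242 = 0.06.

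**Step 4: effect on the graph rule.** Graphs with more than two lags run from X = Month 3 to X = Month 30, ten in all. Three of them (X = Months 3, 6, 9) approach Month 12 from before. At n = 245, the chance that the Month 15 value on these curves exceeds the Month 12 value rises from 30–40% to 58–64% (pure AR(1): from 10–23% to 23–34%). The SAP gives no size for a bump. Taking a rise of 0.05 or more, the chance that at least half of the ten graphs are flagged goes from 31–67% to 50–75% (pure AR(1): 3% or less either way).

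**Step 5: precision.** Take a true correlation of 0.25, reduced in the ratio 0.19/0.30 to 0.16. With a Fisher-z interval at n = 245, variance 1.06/242, the chance that the 95% CI excludes 0 falls from 97% to about 67%. The plan sets no hypothesis for this endpoint, so this only illustrates how the reported interval would look.

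**The case against.** The strongest reply is that nothing is hidden. The Month 3 to 12 correlations are already computed in FAS Period 1, so the association in all treated patients will be reported. After Month 12 only responders remain under observation, and Protocol 13.2 itself builds the entire-study FAS from markedly improved patients (there, those randomised to IKERVIS). A coefficient in a stated population is restricted, not wrong. This stands for pairs after Month 12, which need a label rather than a repair. It does not justify recomputing the Month 3 to 12 pairs in the selected set, where the unselected answer exists and the selected one is lower by construction.

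A second reply concerns the remedy. Joining FAS Period 1 values to selected values in one curve would create a step (in a model with AR(1) plus measurement error, about 0.26 at Month 12 followed by 0.16 at Month 15), and pairs crossing Month 12 are the ones that speak to long lags. The step is avoided by not joining the two sets. The loss of long-lag pairs from the count is a real cost.

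Three stronger readings are tempting and not supported:

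- *Selection alone would produce a lag conclusion.* It bends three of ten graphs, and the rule needs five. The rule already fires often without selection under several structures, so correcting the population does not repair the rule.
- *Month 12 is always the lowest point, or the whole three-year correlation is lost.* Under pure AR(1) the lowest values come after Month 12, and losses away from Month 12 are modest.
- *The markedly improved subgroup in SAP 8.3 is truncated in the same way*, since "Efficacy analysis of Period 1 will be repeated using this subpopulation". SAP 6 defines that subgroup by improvement at any time in Period 1, not at Month 12. In a no-lag run its same-visit values at Months 3 to 12 were level at 0.27–0.29, against 0.31 in all patients, with no dip at Month 12.

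**Conclusion.** The selection is certain from the documents: every Entire Study correlation is computed in patients who passed the Month 12 CFS rule, and no SAP text corrects for it. At the planned 70% retention the Month 12 same-visit coefficient is lowered by roughly a quarter to 40%. Other visits lose less.

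The size rests on the assumed unselected correlation of 0.2–0.5, though the proportional loss changes little across that range. The shape of the bend depends on the unknown between-visit correlation and is secondary: it adds to false lag signals and does not decide the conclusion alone. The Period 1 analysis in FAS Period 1 is unaffected. The difference between protocol and SAP on whether the entire-study set includes the vehicle arm is a separate matter. Because this is a primary analysis and the remedy is cheap, the SAP should be changed.

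**What to change.** In SAP 8.1.1 and Table 4:

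1. Take every pair with both visits at or before Month 12 from FAS Period 1, and do not recompute these pairs in FAS Entire Study.
2. Label every Entire Study pair that includes a visit after Month 12 as describing Month 12 responders only. Pairs from X = Month 15 onward remain indirectly truncated, so they need the label too.
3. Show pairs that cross Month 12 (X at or before Month 12, X+i after it) separately, not joined to the FAS Period 1 curve, and leave them out of the half-of-the-graphs count. State the resulting denominator. Within the randomised set, removing X = Months 3, 6, 9 and 12 leaves 10 − 4 = 6 graphs, X = Months 15 to 30.
4. Optionally, add as a sensitivity analysis a joint likelihood model of CFS and SANDE changes on all FAS Period 1 patients. Selection depends on an observed value, so such a model can allow for it. For X = Month 3 and r = 0.5 it returned 0.50, 0.32, 0.28, 0.26, 0.23, 0.21 at Months 3 to 18, equal to the unselected values, against 0.48, 0.27, 0.22, 0.15, 0.16, 0.15 in the selected set. That check used continuous normal scores, so its performance on graded CFS remains to be shown.

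The cost is SAP wording and a change of analysis set for some rows of Table 4, with no new data. The three-year display no longer has a single population, and long-lag pairs crossing Month 12 become descriptive.
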